2.6.1 Collection of Tumor Tissue

In order to explore the determinants of response and resistance to combination durvalumab and tremelimumab therapy, archival tumor tissue will be collected at baseline from all patients enrolling to the trial. In addition, mandatory pre- and on-treatment fresh tumor biopsies will be obtained whenever clinically feasible from all patients enrolled. An optional final biopsy will be offered to all patients at the time of disease progression. The genetic and immune characteristics identified in the tumor tissue will be correlated to clinical outcome.

Analysis of tumor tissue samples taken at distinct points enables addressing of key questions including: (1) the genomic lesions and immune cell presence at baseline in samples studied and their potential impact upon response, (2) the identification of immediate gene pathways or immune expression programs activated by tumors following durvalumab and tremelimumab combination therapy, and (3) mechanisms of acquired resistance to therapy.

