9.1.2 Fresh Tumor Biopsies

Mandatory pre- and on-treatment fresh tumor biopsies will be obtained from patients enrolling to the trial. In the event the biopsy is not clinically feasible in the opinion of the treating investigator or interventionalist performing the procedure, exceptions to one or both fresh biopsy requirements are possible after discussion with the principal investigator.

The pre-treatment biopsy should be obtained following consent and prior to the first dose of any study medication (prior to Cycle 1 Day 1). The on-treatment biopsy may be obtained anytime between Cycle 2 Day 1 (after completion of the study medication infusions) to Cycle 2 Day 8.

An additional optional biopsy at the time of disease progression will also be offered to patients if deemed clinically feasible by the treating investigator. In patients undergoing re-treatment with tremelimumab, the time of progression biopsy may be obtained either prior to the initiation of re-treatment or upon progression following re-treatment. Preferably, time of progression biopsies should be obtained prior to the initiation of another cancer treatment. However, in the event that it is not possible to perform the biopsy before another treatment is begun, the biopsy can be obtained up to 60 days after the last dose of study medication.

Pre- and on-treatment core biopsy samples a minimum of 2 cores should be collected, if clinically feasible. A 16-18 gauge needle are preferable, but a 20 gauge core needle biopsy is also acceptable. For more information, please refer to the Thoracic Oncology Program 16-549 Biopsy Collection Guidelines. In the event that not enough tissue is obtained, priority should go to immune profiling.

If a core biopsy is judged to be too unsafe or difficult for the participant in the opinion of the treating investigator, a fine needle aspirate (FNA) or cytology sample can also be collected. The goal for a thoracentesis or paracentesis procedure will be 500 - 1000 mL collected in a standard collection tube. The goal for an FNA will be three distinct passes. Less than the goal amount of tissue is acceptable for any of the biopsy collection methods, and should be based upon the clinical judgment of the treating investigator and the clinician performing the procedure.

All tumor biopsy samples should be labeled with the protocol number, study subject number, date of collection, and identified as either "pre-treatment," "on-treatment," or "time of progression."

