13. STATISTICAL CONSIDERATIONS

We will employ a Simon's 2-stage design to test the hypothesis that durvalumab and tremelimumab improve response rates in this patient population to 35%, compared to a historical control rate of 16%. In the first stage we will enroll 19 patients, and if 4 or more patients among those 19 respond to therapy (with either a complete or partial response), we will open the 2nd stage of accrual to enroll an additional 21 patients, making a total sample size of 40 patients. If fewer than 4 patients experience a response in the first stage then the study will be stopped. In order to declare study success, a total of 10 or more responses must be observed among all 40 study participants. This design has a 0.64 probability of stopping early under the null, and has 90% power while maintaining an overall one-sided type I error rate of 0.08.

Statistical Analysis Plan for Correlative Studies:

Data from correlative studies will be summarized using descriptive statistics. Associations

between immune cell subsets, immune marker expression, and the characteristics of the PBMCs will be compared to clinical outcome, will be summarized by descriptive methods, and may be explored graphically.

We assume that 80% of patients (n=32) will be successfully biopsied at multiple time points and have tumors that yield valid results from the laboratory.

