When comparing baseline, on-treatment, and time of progression genomic and immune results, it is of interest to identify new alterations that were not present at baseline. Initial analyses of these data will utilize tests for association comparing the frequency of a particular genomic or immune aberration at baseline, on-treatment, and at progression (for example, using McNemar's test) and association between alterations and baseline characteristics (for example, using Fisher's exact test). For non-normal distributions (% T-cell infiltrate), we will explore associations with the presence or absence of a genomic or immune feature using non-parametric analysis for subgroup comparisons (Wilcoxon rank-sum or Kruskall-Wallis). Fisher's exact test will be used for discrete comparisons of categorical immune and clinical variables (such as PD-L1 positive vs. negative). More sophisticated analyses may include multivariable logistic regression modeling and/or competing risks analysis, however it is expected that analyzable results will not be obtained from all patients (either due to things like assay failure, inability to biopsy at progression due to poor patient health, etc).

With at least 32 patients included in the correlative analysis, this sample size provides 84% power to detect differences in the rate of another binary variable (such as baseline characteristics or abnormality) with frequencies of 8% and 60%, respectively, while testing with a one-sided 0.10-level Fisher's exact test; this also assumes that the underlying prevalence of the genomic marker is 50%, thus splitting the cohort into two groups with 16 patients in each. It is worth noting that the Fisher's test for association between the presence/absence of baseline samples and resistant samples assumes independence between those samples. Given what is known about tumor heterogeneity, the likelihood that the cancer may be altered genomically over time and due to therapy, and the low chance that the same area of a patient's tumor will be biopsied at both time points, this seems like a reasonable assumption.

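### Section 13 defends treating baseline and progression samples from the same patients as independent; the samples are paired, so the defence should be deleted and the paired test stated (minor)

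*Combined protocol and SAP*

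**What the plan says.** All of this is in Section 13 of the combined protocol and SAP, under the plan for correlative studies, unless another section is named.

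- **The question is within-patient change:** "it is of interest to identify new alterations that were not present at baseline".
- **A paired test is named, as an example:** initial analyses are to use tests "comparing the frequency of a particular genomic or immune aberration at baseline, on-treatment, and at progression (for example, using McNemar's test").
- **Fisher's exact test is assigned to between-patient questions:** alterations against baseline characteristics, and categorical immune and clinical variables.
- **A caveat follows the power statement:** "Fisher's test for association between the presence/absence of baseline samples and resistant samples assumes independence between those samples". It rests on tumour heterogeneity, on genomic change under therapy and over time, and on the expected biopsy sites: "the low chance that the same area of a patient's tumor will be biopsied at both time points, this seems like a reasonable assumption".
- **The same patients supply the samples:** "We assume that 80% of patients (n=32) will be successfully biopsied at multiple time points".
- **The progression biopsy is optional.** Section 9.1.2: "An additional optional biopsy at the time of disease progression will also be offered to patients if deemed clinically feasible". Section 2.6.1 also calls it optional. Section 13 itself foresees "inability to biopsy at progression due to poor patient health".

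Sections 1.4 and 13.1 list the resistance and genomic objectives as exploratory. The last paragraph of Section 13.3 describes subset analyses, including correlatives, in the same way.

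**The concern.** The section points two ways on the same samples. It illustrates the time-point comparison with a paired test, then defends the assumption that an unpaired test would need. The defence does not work. Sampling another area of a tumour may lower the correlation between a patient's two results, but they remain two results from one patient. Because McNemar's test is given only as an example, an analyst could cite the caveat to justify an unpaired comparison.

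What is at stake is the reading of the acquired-resistance results. An unpaired comparison of a within-patient question can miss real gains. If the two sets also contain different patients, it can mix change over time with differences in who was biopsied again.

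**Working it through.** **Inputs.** The plan gives 32 patients with samples at multiple time points, and one-sided 0.10 as the level for Fisher's test. It gives no prevalence, gain, loss or correlation for the time-point comparison, so those below are assumptions. Using 0.10 for McNemar is also an assumption. Gain and loss are shares of all patients. For baseline against progression, 32 pairs is a best case because the progression biopsy is optional. All results are exact enumerations unless marked otherwise.

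**The plan's own figure.** The 84% power in Section 13 is for a between-patient split of 16 and 16, not for time points, so it does not bear on this point. (Exact enumeration of that design gives 95.9% at the stated level, and 84.0% at one-sided 0.025. That is a separate matter and nothing below uses it.)

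**Step 1: complete pairs, 30% positive at baseline, 20% gain, no loss.**

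Exact McNemar with g gains and no losses has p = (1/2)^g. Three gains give 0.125 and four give 0.0625, so four are needed. Power is P(Binomial(n, 0.20) ≥ 4): 0.907 at n = 32 and 0.121 at n = 10.

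Fisher's test on the two sets as unpaired groups uses the hypergeometric upper tail. With 10 of 32 positive at baseline (0.30 × 32 = 9.6), 16 of 32 at progression gives p = 0.101 and 17 of 32 gives p = 0.064. Seven gains are needed where McNemar needs four.

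| Pairs | Unpaired Fisher | Exact McNemar |
|---|---|---|
| 32 | 54.7% | 90.7% |
| 24 | 36.5% | 73.6% |
| 16 | 20.8% | 40.2% |
| 10 | 12.1% | 12.1% |

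With 20% gain and 5% loss, 32 pairs give 33.8% against 53.8%. At 0% baseline prevalence the tests do not differ at 32 pairs (90.7% each).

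**Step 2: false-positive rate with complete pairs.** Take 32 pairs, 30% prevalence at both times and correlation ρ. Then P(both positive) = 0.09 + 0.21ρ, and each discordant cell is 0.30 minus that. At ρ = 0.6 these are 0.216 and 0.084.

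| ρ | Unpaired Fisher | Exact McNemar |
|---|---|---|
| 0 | 6.5% | 6.0% |
| 0.4 | 2.5% | 5.0% |
| 0.6 | 0.9% | 3.5% |

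Both stay under 10%. With complete pairs the cost of ignoring pairing is power, not false positives.

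**Step 3: all 32 baseline samples against m progression samples missing at random.** The plan does not say which baseline samples would enter an unpaired test; this is one possibility. Rates are as in step 1, with McNemar on the m pairs.

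| m | Fisher, all samples | McNemar, pairs |
|---|---|---|
| 24 | 47.7% | 73.6% |
| 16 | 38.5% | 40.2% |
| 15 | 37.9% | 35.2% |
| 10 | 27.5% | 12.1% |

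The two break even at 15 to 16 progression samples. Below that the unpaired test has more power because it keeps baseline samples that have no partner. At 0% baseline prevalence it also leads at larger m (m = 16: 64.8% against 40.2%).

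**Step 4: the same comparison, but re-biopsy depends on marker status.** Assume that no tumour changes, 30% are positive, and 60% of positive but 18.9% of negative patients are re-biopsied. The expected number of progression samples is 32 × (0.30 × 0.60 + 0.70 × 0.189) = 10.0. Fisher's false-positive rate is 45.4%. At 50% and 23.2% it is 18.7%; at an equal 31.25% it is 1.1%; in the reverse direction (20% and 36.1%) it is 0.1%. These figures assume perfect agreement between a patient's two results. By simulation at a within-patient correlation of 0.6, 45% falls to about 21% and 19% to about 11%. McNemar's 0% under perfect agreement is built in, since no pair is discordant.

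**The case against.** The strongest reply is that the plan already names the right kind of test. McNemar's is its example for time points, and every use of Fisher's test that it assigns is between patients. The caveat schedules no analysis, discloses its assumption and is hedged. Its wording does not define a table. Harm follows only if someone uses it to displace the named test, and the work is exploratory. Nor is McNemar uniformly better: with few progression samples missing at random, step 3 favours the unpaired test. Prescribing McNemar also goes further than deleting a faulty rationale.

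Most of this stands and sets the size of the point. It does not rescue the caveat, whose reasoning is wrong for samples from the same patients. Because the paired test is only an example, the section leaves the choice unsettled.

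Three stronger readings are tempting, and the documents do not support them.

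- **That the plan will compare all baseline patients with a selected progression subset.** No section says so; a comparison restricted to patients with both samples is equally possible.
- **That the caveat implies a high false-positive rate.** The figures in step 4 need re-biopsy to depend on marker status and, at their largest, perfect agreement between biopsies. Section 13 gives poor health as a reason for missing samples but does not link it to marker status.
- **That Fisher's test would be run on baseline status by progression status within patients.** Independence would then be the null hypothesis and the test would measure persistence. The caveat calls independence an assumption, so this reading fits its words poorly.

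**Conclusion.** The rationale is wrong as written: the samples are paired, and the reasons given do not make them independent. With complete pairs and positive correlation the unpaired test is conservative. Its power loss ranges from 36 percentage points at 32 pairs (90.7 − 54.7) to none at 10 pairs, at the assumed 30% prevalence, 20% gain and no loss. With incomplete pairs the direction depends on which samples enter and why others are missing, neither of which the plan settles. The conclusion that the samples are paired rests on the documents alone; every power and error rate above rests on assumed values.

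This is a minor correction. The primary endpoint, sample size, stopping rule and safety analyses are untouched.

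**What to change.** 1. Delete the two sentences on independence that close the correlative power paragraph in Section 13.
2. State that each pairwise time-point comparison of a binary feature uses McNemar's test (exact) on patients with both samples, and report the number of pairs, gains and losses beside each result.
3. Keep Fisher's exact test for between-patient comparisons, as Section 13 already assigns it.
4. Label any unpaired comparison of time points as descriptive, and state that it ignores pairing and assumes that missingness is random.

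The cost is wording only; no new samples are needed. The analytic downside should be stated: patients without a progression sample drop out of the paired test, which lowers its power when such samples are few (12.1% against 27.5% with 10 progression samples in step 3).

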13.1 Study Design/Endpoints

Primary Efficacy Measure:

• Investigate the ORR in patients with malignant pleural mesothelioma.

Secondary Efficacy Measures:

- Evaluate the safety and tolerability of tremelimumab in combination with durvalumab.
- Determine the OS, PFS, and DoR in patients with malignant pleural mesothelioma.

Exploratory Endpoints:

- Investigate the immunologic determinants of primary response and resistance to tremelimumab in combination with durvalumab in malignant pleural mesothelioma
- Investigate the immunologic mechanisms of acquired resistance to tremelimumab in

combination with durvalumab

• Investigate genomic correlates of response to tremelimumab in combination with durvalumab

13.2 Sample Size, Accrual Rate and Study Duration

The planned total sample size is 40 patients in this single-arm, phase 2 study of durvalumab and tremelimumab in patients with malignant pleural mesothelioma. The planned accrual rate is approximately 5 patients per quarter. Up to an additional year of follow-up will be required on the last participant accrued to observe the patient's response and survival following study therapy, for a total study length of approximately three years.

Table 10: Accrual Targets								
Ethnic Category	Sex/Gender							
	Females			Males				Total
Hispanic or Latino	1		+	3		=	4	
Not Hispanic or Latino	9		+	27		=	36	
Ethnic Category: Total of all subjects	10	(A1)	+	30	(B1)	=	40	(C1)
Racial Category								
American Indian or Alaskan Native	0		+	0		=	0	
Asian	1		+	2		_	3	
Black or African American	1		+	2		_	3	
Native Hawaiian or other Pacific Islander	0		+	0		=	0	
White	8		+	26		=	34	
Racial Category: Total of all subjects	10	(A2)	+	30	(B2)	=	40	(C2)
		(A1 = A2)		(B1 = E	32)			(C1 = C2)

13.3 Analysis of Primary and Secondary Endpoints

The primary and secondary analyses will include all eligible patients who started assigned therapy. The exception to this includes the planned analysis of toxicity data, which will include all patients who received study drug regardless of eligibility. Response will be assessed using the modified RECIST criteria for mesothelioma; toxicity will be graded using CTCAE v. 4.03.

For the analysis of the response efficacy measures, participants will be censored if they are alive and without disease progression at the date of the last disease evaluation. In the case of OS, participants will be censored if they are living at the date last known alive.

Time-to-event data, such as PFS and OS, will be estimated using the Kaplan-Meier method, and Cox proportional hazards models will be used to estimate hazard ratios. Comparisons of groups will be made using the logrank test and Cox modeling.

Categorical data, such as response rates (CR+PR) and toxicity, will be compared using Fisher's exact tests with a one-sided type I error rate of 10%; multivariable logistic regression modeling will be used to adjust for the effect of any covariates that are associated with these categorical outcomes. Though none are currently planned, any continuous outcomes will be analyzed using Wilcoxon rank sum test, and multivariable linear regression models may be used to adjust for multiple associations with outcome.

Modeling procedures will implement backward selection; variables significant at the 0.10 level in the univariate setting will be chosen for inclusion in an initial full model, and at each step the least significant variable will be removed from the model. Only those covariates with p<0.05 will remain in any final models, unless there are factors identified by the study team as crucial to model interpretation.

Point estimates of all endpoints will be accompanied by the corresponding two-sided 80% confidence intervals. The method of Atkinson and Brown will be used for the estimation of the confidence interval for response.

In the event that there are missing data, no imputation of the missing data will be conducted. We will assume that data are missing at random and will conduct all analyses as originally planned because we do not anticipate an excess of missing data.

Subset analyses are planned for all known prognostic factors, such as performance status, age, sites of metastases, gender, etc. Subset analyses of all variables, including correlatives, are considered to be exploratory in nature.

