1.3 Secondary Objectives

- Determine the progression free survival (PFS) rate, defined as the time from registration to disease progression or death due to any cause. Participants alive without disease progression will be censored at date of last disease evaluation.
- Determine the overall survival (OS) rate, defined as the time from registration to death due to any cause (or censored at date last known alive).
- Determine the duration of response (DoR), defined as the time from documentation of tumor response to disease progression (or censored at the date of last disease evaluation).
- Evaluate the safety and tolerability of tremelimumab in combination with durvalumab.

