2.6.2 Non-Invasive Immunoprofiling

Peripheral blood mononuclear cells (PBMCs) will be collected from whole blood to assess immune cell populations and cytokines. Surface staining with a panel of antibodies and intracytoplasmatic cytokine staining followed by flow cytometry will be performed on the samples. Different T cell populations, their activation status, and the production of different cytokines as well as other immune cell populations including myeloid-derived suppressor cells (MDSCs) will be characterized. MDSCs are a heterogeneous group of immature cells which are greatly expanded in experimental models of cancer. Studies in humans have reported increased frequencies as well as immune-suppressive properties in some of the myeloid-derived subsets of MDSCs present in the peripheral blood of patients with various forms of cancer, including mesothelioma^{42,43}. To further explore the relationship of immune cell populations and their potential correlation to clinical outcomes, peripheral blood levels will be serially collected from patients enrolled to the trial.

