9.2 Laboratory Correlative Studies

Peripheral blood mononuclear cell (PBMC) samples will be collected at baseline (on Cycle 1 Day 1 prior to the first dose of study medication), on Cycle 2 Day 1, at visits following restaging scans, and at the off study visit. Samples collected on days where study medication dosing will occur can be collected anytime pre-dosing.

Collection and Shipping Procedure:

- 1. Blood samples should be labeled with the protocol number, study subject number, date of the draw, visit day (i.e. "C1D1" or "C2D1"), and labeled as "PBMC."
- 2. Draw venous blood into four 10 mL EDTA tubes and immediately gently invert the tube 3-4 times.
- 3. Send tubes to the CIO lab for processing within 6 hours of blood draw (tubes sent outside of this window due to shipping or scheduling difficulties will not be considered protocol violations but every effort should be made to get the samples to the laboratory within 6 hours of draw time):

ATTN: CIO Laboratory Manager Center for Immuno-Oncology Laboratory [name]

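### If markers from post-restaging, off-study or serial blood draws are compared on PFS or OS from registration, a marker with no effect can look predictive

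*Combined protocol and SAP*

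**What the plan says.** - **Clock.** Section 1.3 has PFS "defined as the time from registration to disease progression or death due to any cause". OS has the same origin: "Determine the overall survival (OS) rate, defined as the time from registration to death due to any cause". Section 11.1.6 repeats both.
- **Method.** Section 13.3 estimates time-to-event data by Kaplan-Meier, then states: "Comparisons of groups will be made using the logrank test and Cox modeling". The trial has one arm, so the groups can only be subsets of patients.
- **Which subsets.** Section 13.3 lists known prognostic factors and adds: "Subset analyses of all variables, including correlatives, are considered to be exploratory in nature".
- **Sampling.** Section 9.2 takes one blood sample "on Cycle 1 Day 1 prior to the first dose of study medication", another on Cycle 2 Day 1, and then more "at visits following restaging scans, and at the off study visit". Restaging is every 8 weeks (Section 11.1). Table 7 also marks a draw on Cycle 3 Day 1, about week 8. The on-treatment biopsy falls between Cycle 2 Day 1 and Day 8 (Section 9.1.2).
- **Purpose.** Section 2.6.2 gives possible correlation with clinical outcomes as the reason that "peripheral blood levels will be serially collected from patients enrolled to the trial". The correlative plan in Section 13 compares immune and blood markers with clinical outcome, by descriptive and possibly graphical methods.

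No section gives a landmark, a time-dependent covariate, or a rule that only baseline values may enter a model timed from registration.

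**The concern.** Two separate biases follow if the stated survival method is applied to the later samples.

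1. **Guaranteed time.** Each further progression-free interval adds a draw. Any summary over draws (ever above a cut-off, peak value, largest change) therefore favours patients who progress late. A clock from registration credits the time they had to survive progression-free, in order to be sampled, to the marker.
2. **Sampling after the event.** A draw that follows a scan showing progression comes after the PFS event, and the off-study draw often will too. Such a value may be a result of progression and cannot be read as a predictor of it.

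At stake is the exploratory aim in Section 1.4, to find immunologic determinants of response and resistance. A null marker could be carried forward as a candidate. The exploratory label covers multiplicity and the strength of the claim, but it does not remove a systematic bias. A Kaplan-Meier plot split by such a marker carries the same bias with no test at all.

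**Working it through.** **The plan's own figures.** Section 13 gives operating characteristics only for the two-stage response design (4 or more of 19 to continue, 10 or more of 40 for success, 16% against 35%). Exact binomial enumeration gives early stopping 0.638 (stated 0.64), power 0.901 (stated 90%) and one-sided error 0.082 (stated 0.08). They reproduce, and this point does not touch them. There is no stated figure for the log-rank or Cox comparisons.

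**Inputs from the documents.** 40 patients, 32 assumed to have usable multi-time-point results; draws at week 4 (28/30.44 = 0.92 months) and at each 8-weekly restaging (56/30.44 = 1.84 months). Accrual at 5 per quarter takes 40/5 = 8 quarters, or 24 months; with up to 12 months more, follow-up is 12–36 months.

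**Assumptions not in the documents.** Exponential PFS with median 3, 5 or 7 months; censoring uniform over 12–36 months; a marker unrelated to outcome, positive at each draw with probability p = 10% or 20% (50% for a single baseline or Cycle 2 value).

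**Mechanism.** With n draws, the chance of being ever positive is 1 − (1 − p)^n. Take p = 0.2 and count post-baseline draws only:
- progression at 1.5 months: n = 1, chance 1 − 0.8 = 0.20;
- progression at 8 months: n = 1 + floor(8/1.84) = 5, chance 1 − 0.8^5 = 0.67.

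The marker carries no information, yet the late progressor is over three times as likely to be positive.

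**Simulation, true hazard ratio 1** (3,000 runs per setting, 32 and 40 patients, PFS; ranges over settings):

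| Grouping | Median HR | Two-sided 5% rejects | One-sided 10% rejects |
|---|---|---|---|
| Baseline marker, from registration | 0.99–1.01 | 6–7% | 10–11% |
| Single Cycle 2 Day 1 value, sampled patients only | 0.99–1.02 | 6% | 10–12% |
| Same, unsampled counted as negative | 0.69–0.83 | 8–20% | 21–43% |
| Ever positive, Cycle 2 plus restaging draws | 0.26–0.42 | 47–96% | 74–99% |
| Same plus baseline draw (p = 20%) | 0.30–0.42 | 64–87% | 84–96% |
| 8-week landmark, clock restarted | 1.01–1.02 | 5–8% | 9–10% |

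**Sensitivity.** Other assumption sets at medians of 3–5 months gave one-sided 10% rejection of about 60–98%, and at the lowest 45–73%, for an ever-positive marker on PFS. For OS, one model (PFS plus an exponential time with a 6-month median, censored at 24 months) gave 21–43%.

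**Sampling after progression.** Take one sample after the first restaging, and let progression at that scan shift the marker by 0.5–1 SD (an assumption). The one-sided 10% log-rank from registration then rejects in about 22–51% of runs, and with the landmark in about 9–12%.

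**Patients lost to the landmark.** The share progressing by week 8 is 1 − 2^(−1.84/median): 35% at 3 months and 23% at 5 months. Of 32 patients that is 0.346 × 32 = 11 and 0.225 × 32 = 7.

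**The case against.** The strongest reply is that the plan never states this analysis. The log-rank sentence sits under primary and secondary endpoints, and the subsets named there (performance status, age, sites of metastases, gender) are ordinarily baseline factors, for which the registration clock is right. Immune markers have their own plan, which is descriptive and graphical with McNemar, Fisher and Wilcoxon-type tests, and with logistic or competing-risks models as options. No ever-positive rule, peak or cut-off across visits is defined. The one-sided 10% level is stated for Fisher's tests only. Sampling at progression also serves the acquired-resistance aim.

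Much of this stands:
- A reader might infer that the plan commits to log-rank groups defined by post-baseline markers, so that worthless markers will be reported as determinants. The documents do not support that. They leave the route open, and the outcome is possible, not certain.
- A reader might also infer that every on-treatment marker is biased. It is not: one Cycle 2 value, or the Cycle 2 Day 1–8 biopsy, compared only among sampled patients behaves like a baseline marker under the null. Counting unsampled patients as negative would bias it, but no such rule is planned, and Section 13.3 rules out imputing missing data.
- The text of footnote G to Table 7, which governs later blood draws, is not readable in the copy reviewed, so any further limit there could not be checked.

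The objection does not close the gap. Correlatives are named among the subset variables, serial blood is collected to be related to outcome, and the only survival comparison on offer is one that fails for later draws.

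**Conclusion.** The concern holds in a conditional form. If markers from post-restaging, off-study or serial blood draws are related to PFS or OS by the log-rank and Cox methods of Section 13.3, timed from registration, a marker with no effect can look strongly predictive. For an ever-positive rule the false-positive rate at a two-sided 5% test was 47–96%, against 5–8% with a landmark. These sizes rest on assumed PFS medians, per-draw positivity and a marker rule that the documents do not give. The bias favoured the marker-positive group in every ever-positive setting tried, but no single percentage should be quoted as this trial's error rate. The OS figures rest on one model and are the least secure.

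The primary response test, the overall PFS and OS estimates, and analyses of baseline markers are untouched. This is an inexpensive clarification of an exploratory analysis that is worth making before the marker data are examined.

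**What to change.** Add a short paragraph to Section 13, cross-referenced from 13.3:

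1. Limit log-rank tests, Cox models and Kaplan-Meier plots timed from registration to baseline markers (archival tissue, pre-treatment biopsy, Cycle 1 Day 1 blood). A single Cycle 2 value may be compared among sampled patients only.
2. For a single marker sampled at or after the first restaging, set a landmark at that visit in advance, allowing for the ±7-day scan window. Include only patients alive and progression-free then, and restart the clock there.
3. For markers summarised over several draws, enter the marker as a time-dependent covariate in the Cox model.
4. Treat draws at or after documented progression as progression samples only.
5. Do not count unsampled patients as marker-negative.

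This needs no new samples, visits or patients. The cost is that patients who progress by the landmark leave that exploratory comparison: about 7–11 of 32 at the first restaging if median PFS is 3–5 months. The landmark result then applies only to patients still progression-free at that visit, and the report should say so.
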